4.0 INTRODUCTION

4.1 Background

Overweight has become an epidemic disease and impairs the health of more than 1.9 billion adults, of whom 650 million are obese, defined by a. BMI of \geq 30kg/m². This represents about 13% of the worlds adult population. 1

Obesity impacts many organ systems. One affected system is the cardiovascular system, including an increased prevalence of heart failure, hypertension and coronary heart disease. Obstructive sleep apnea and asthma are also common in the obese. Non-alcoholic fatty liver disease (NAFLD), including non-alcoholic steatohepatitis (NASH), is on the rise and may become the leading cause of cirrhosis and hepatocellular carcinoma. Psychosocial and psychiatric consequences of obesity are also increasing.²

Dual agonists have been developed that co-target the glucagon and glucagon like peptide (GLP-1) receptors for obesity treatment. Additionally, triple agonists, which have added a gastric inhibitory polypeptide receptor (GIPR) agonist to the combination, are under development in early phase clinical studies.

HM15211 is a novel long-acting triple incretin agonist. It is a chemical conjugate of a chimeric peptide (GLP-1/Glucagon/GIP triple agonist; named as TA15211) and human immunoglobulin G4 Fc fragment (named as HMC001) linked via a bifunctional Maleimide-Polyethylene glycol- Aldehyde (MAL-PEG-ALD) linker molecule.

TA15211 is produced by chemical synthesis and the quality of TA15211 is controlled by complying with in-house specification. The HMC001 moiety was derived from the constant region of human immunoglobulin G4 fragment and produced in the transformed E. coli as an inclusion body. The inclusion body was purified after successive refolding and purification steps, and the quality of HMC001 was controlled by in-house specification. Human immunoglobulin G4 Fc fragment (HMC001) was chosen as the stabilizing agent because it is the most prevalent blood protein and has an in vivo half-life of several weeks without effector functions including antibody dependent cellular toxicity (ADCC) and complement dependent cytotoxicity (CDC). The linker is a 10 kDa polyethylene glycol (PEG) with bifunctional reactive groups (maleimide aldehyde reactive groups at individual ends, MAL-PEG-ALD). The conjugation of TA15211 and HMC001 is carried out through the formation of a thioether and amine bond between hetero-bifunctional MAL-PEG-ALD, Cys40 in TA15211, and the N-terminal amino acid in HMC001.

HM15211 is a long-acting GLP-1/Glucagon/GIP triple agonist with extended half-life through reduced renal clearance and possibly by vascular endothelial recycling via FcRn binding. HM15211 showed triple-agonistic properties with potent glucagon activity in addition to balanced GLP-1 and GIP activity.

According to series of in vivo pharmacologic studies, HM15211 can be an attractive treatment option for obese patients based on its potent body weight loss efficacy from

energy intake inhibition and energy expenditure enhancement. Glucagon activity provides potent body weight loss primarily from fat mass reduction as shown in efficacy studies in diet-induced obesity (DIO) mice. Furthermore, GLP-1/GIP activities negate a possible hyperglycemic risk as demonstrated in intra-peritoneal glucose tolerance test (ipGTT) studies in normal and DIO mice.

Above all, liver preferential distribution, and following hepatic lipid metabolism improvement, renders HM15211 a suitable therapeutic option for NASH and hepatic fibrosis. Therefore, HM15211 is expected to have favorable therapeutic profiles in both, obesity and NASH as well as convenience in its clinical dosing regimen.

For further information please refer to the Investigator's brochure (IB).

4.2 Rationale for the Proposed Study

The aim of this first-in-human, single ascending dose study is to investigate safety and tolerability of the drug as well as the PK profile in healthy obese subjects. Five cohorts of 8 subjects will investigate the drug, and will include a placebo comparison in each cohort.

Based on the pre-clinical data and existing research on the drug components/ drug class that exists in the public domain, as well as the proposed monitoring conditions of the proposed inpatient study, it is reasonable and appropriate to investigate the study drug in the intended potential target population. Healthy obese subjects will ensure that a robust and relevant set of safety and PK data can be generated to inform the design of subsequent clinical studies.

4.3 Summary of Pre-Clinical Studies

To date, no human studies have been conducted with HM15211.

In vitro activity of HM15211 was evaluated using respective receptors, human GLP-1 receptor (hGLP-1R), human glucagon receptor (hGlucagonR), and human GIP receptor (hGIPR). HM15211 showed dose-dependent activation of all three receptors with potent glucagon activity in addition to balanced GLP-1 and GIP activity. Simultaneous activation of three incretin receptors could provide synergistic metabolic benefits on body weight loss and lipid profile improvement whilst avoiding hyperglycemic risk.

Further in vitro studies confirmed, that since HM15211 includes an aglycosylated Fc moiety derived from human IgG4, it shows minimal immune-mediated effector functions. In addition, due to Fc moiety, HM15211 retained pH-dependent FcRn binding property, which is essential for vascular endothelial recycling.

In vivo pharmacology studies using obese mice showed that HM15211 enables potent body weight loss from both, food intake inhibition and enhanced energy expenditure. The body weight loss was mainly from fat mass reduction, along with lowered serum lipid profile. Glucagon action increased energy expenditure and thus enhanced body weight loss and hyperglycemic risk by glucagon was effectively buffered by actions of GLP-1/GIP. In NASH induced models, HM15211 effectively reduced hepatic triglycerides

(TG), oxidative stress and inflammatory markers. Furthermore, HM15211 treated animals showed significant reduction in NAFLD activity score and hepatic fibrogenic markers, suggesting HM15211 as an effective pharmacotherapy for NASH with hepatic fibrosis.

Safety pharmacology studies were conducted to evaluate the effects on the cardiovascular, respiratory, central nervous systems and in vitro hERG channel assay. No significant effect was observed in the safety pharmacology studies and in vitro human ether-a go-go related gene (hERG) channel assay.

In pharmacokinetic studies, HM15211 exhibited a prolonged half-life (t½) after subcutaneous (SC) or intravenous (IV) dosing, which ranged from approximately 42.7 to 85.6 hours in mice, 74.7 to 86.0 hours in rats, and 35.7 to 79.7 hours in dogs, indicating that HM15211 is a long acting triple-agonist. HM15211 is preferentially distributed in the liver, making HM15211 a favorable treatment option for dysfunction in lipid metabolism specifically in the liver.

The toxicity studies of HM15211, repeat dose toxicity up to 4 weeks in rats and monkeys, and in vitro genotoxicity studies, were conducted. Local tolerance of HM15211 was investigated in 4-week repeated rat and monkey studies. Additional studies were conducted with HMC001 (inactive ingredient) in rat and monkey up to 4 weeks repeat dose toxicity studies.

No target organ was identified during the 4 weeks repeat dose toxicity studies of HM15211. All changes were completely or partially reversible during the recovery period.

The majority of findings were related to fasting effect or pharmacological effect of glucagon. No adverse test article-related findings at the injection sites were noted. No adverse events were observed in HMC001 studies.

4.4 Rationale for Starting and Maximum Dose

The proposed starting dose of HM15211 is 0.01mg/kg, selected based on the results of the 28 days toxicology assessments of HM15211 in monkeys and rats, and the application of an additional safety factor, as described in Table 4-1 below.

Table 4-1 Starting Dose Calculations

Species	28-day Toxicity Study NOAEL (mg/kg)	HED (mg/kg)	Planned Starting Dose	Safety Margin vs. NOAEL HED
Rat	0.4	0.07	0.01	7
Monkey	2	0.7		70

The NOAEL was 0.4 mg/kg in rats and 2 mg/kg in monkeys. For conversion to a human equivalent dose (HED), these values were divided by 6.2 for rats and 3.1 for monkeys, resulting in a HED of 0.07 mg/kg for rats and 0.7 mg/kg for monkeys. The starting dose of 0.01 mg/kg in this clinical study is approximately 1/7th of the NOAEL for rats and 1/70th of the NOAEL in monkeys during the 28-day toxicity evaluation of HM15211. Additionally, the starting dose of 0.01 mg/kg is between the ED₁₀ pharmacologically active dose for mice (0.013 mg/kg) and rats (0.007 mg/kg). 5.6

The maximum human dose is determined by the exposure seen at the NOAEL in the 4-week toxicology study in the rat which corresponds to approximately 0.16 mg/kg in a human according to PK prediction. Dose escalation will be determined in safety review and dose escalation meeting by Sponsor and Investigator and will be based on clinical safety and available PK data.

4.5 Dose Escalation Algorithm

The proposed dose escalation algorithm for HM15211 may include the following steps:

Table 4-2 Sample Allocation and Dose Escalation

Cohorts	Number of Subjects	Treatment Period	
Cohort 1	N=6	HM15211- 0.01 mg/kg	
	N=2	Placebo	
Cohort 2	N=6	$HM15211 \le 0.02 \text{ mg/kg}$	
	N=2	Placebo	
Cohort 3	N=6	$HM15211 \le 0.04 \text{ mg/kg}$	
	N=2	Placebo	
Cohort 4	N=6	$HM15211 \le 0.08 \text{ mg/kg}$	
	N=2	Placebo	
Cohort 5	N=6	$HM15211 \le 0.16 \text{ mg/kg}$	
Conort	N=2	Placebo	

Each subject will be randomized to HM15211 or placebo according to the table above. The dose will be 0.01 mg/kg, based on the body weight measured prior to dosing. For dose calculation and rounding, please refer to the Operational Manual/Pharmacy Manual.

After at least 6 subjects ($n \ge 4$ subjects on active drug HM15211) in each cohort have completed at least Day 10, safety and available PK data will be reviewed and a dose decision/ dose escalation decision for the subsequent cohort will be made by the Sponsor and the Investigator. Doses between cohorts will not exceed a 2-fold increase relative to the specified doses stated in the Table 4-3 above. Following the dose escalation decision, the procedures for the subsequent cohorts will be identical to those described above.

Adjustments to the procedures/cohorts may occur after the review of available safety and PK data:

- Adjustments to the number of study cohorts may occur: Additional cohorts may
 be enrolled and proceed at a higher or a lower dose. If deemed appropriate by the
 investigator and sponsor, there may be more than one cohort investigated at the
 same dose level.
- Adjustments to the 24-hr BP and HR monitoring: After the evaluation of the first cohort, tests may be rescheduled, or measurement periods may be focused on specific days to capture the 24-h measurement around the PK_{peak}.
- Adjustments to the visit schedule: If PK data suggest, additional sampling times and/or outpatient visits may be added to the study schedule.

5.0 STUDY OBJECTIVES

5.1 Primary Objectives and Endpoints

To assess safety and tolerability of HM15211 after single SC doses, in regard to:

- Incidence of adverse events
- Incidence of clinical laboratory abnormalities (including serum amylase, serum lipase, coagulation, thyroid stimulating hormone (TSH), serum calcitonin)
- Immunogenicity (Anti-drug antibodies [ADAbs], neutralizing anti-drug antibodies [nAbs], anti-polyethylene glycol antibodies [anti-PEG])
- Change from baseline in vital signs (blood pressure, respiratory rate, temperature, and heart rate) measurements
- Incidence and severity of clinical findings on physical examination
- Injection site reaction
- Change from baseline in 12-lead ECG parameters; the primary ECG endpoint will be QTcF
- Blood pressure (BP) assessed by 24-hour ambulatory blood pressure monitoring (ABPM); (Mean day- and night time systolic/diastolic BP)
- Heart rate activity assessed by 24-hour ambulatory electrocardiography monitoring (Holter ECG); (Heart rate [HR] and heart rate variability [HRV], e.g. mean heart rate, difference between day and night HR, mean normal [NN] intervals, standard deviation of all NN intervals [SDNN])

To assess the pharmacokinetic (PK) profile of HM15211 after single SC doses in regards, but not limited to:

- Maximum concentration (C_{max})
- Time to reach Cmax (T_{max})
- Total area under the concentration time curve (AUC), including AUC_(0-inf)
- Apparent terminal half-life (t_{1/2})
- Apparent clearance (CL/F)
- Apparent volume of distribution at terminal phase (Vz/F)
- Terminal elimination rate constant (k_{el})

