6.3 Rationale for Study Design and Endpoints

This SAD study will assess the safety and tolerability as well as PK of HM15211 as primary objectives.

Cohorts will be assessed in ascending order, but may overlap, to determine a clinically appropriate dose for the subjects and will include the comparison with placebo.

Randomization is used to avoid bias introduced through an association between study drug allocation order and subject characteristics.

A double-blind design has been chosen to avoid bias and to maintain the blind between the administration of the study drug and placebo.

Healthy obese subjects will participate in the study, as these subjects are an important target population for the novel triple agonist. Enrollment criteria will favor the target population, as body mass index will be limited to ≥ 30 to ≤ 40 kg/m².

After PK modeling, C_{max} is expected to be reached approximately 3 days after dosing. As this is a first-in-human study, measurements for the assessment of cardiovascular events will start right after dosing and will continue until Day 4. After evaluation of the PK values in the initial cohort(s), the monitoring period will be adjusted, to ensure that the 24-h period around the PK_{peak} is captured.

The proposed PK endpoints are well-established, commonly used parameters to characterize pharmacological profiles of drugs. For the PK endpoints, blood samples for determination of HM15211 will be analyzed using a validated assay.

This is an exploratory study. No formal sample size calculation and no statistical hypothesis testing will be performed.

The study will be conducted at a specialized early phase research centre, where the subjects will be under supervision of physicians, research nurses and additional medical staff experienced in conducting early phase clinical studies investigating new metabolic compounds.

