9.1.6 Vital Signs

Vital signs will include body temperature (*aural*), supine and standing blood pressure (supine BP after 5 minutes resting, standing BP within 3 minutes in upright position), respiration rate and pulse rate (after 5 minutes resting). Vital sign measurements will be performed at days indicated in the Table 16-1.

Body temperature: Assessments will be performed once daily, as stated in the Table 16-1. Measurements may be taken more frequently, if deemed necessary by the Investigator. Measurement on Day -1 will be performed as baseline assessment. Measurements will continue throughout the study. Timepoints must not interfere with ABPM measurements.

Blood pressure:

Supine and standing assessments will be performed. Measurements will be taken once at Screening and once on Day -2 and twice (morning and evening) on Day -1. The rest of the measurements will follow the following sampling schedule: On Day 1, measurements will be performed pre-dose and at 4, 8 and 12 hours post-dose. On Day 2 at 24 and 36 hours, on Day 3 at 48 hours, on Day 4 at 72 hours, on Day 5 at 96 hours, on Day 6 at 120 hours, on Day 7 at 144 hours post-dose with a sampling window of \pm 15 min for each timepoint. Additional measurements will be taken on Day 10 at 216 hours (\pm 1 day), on Day 17 at 384 hours (\pm 1 day), and on Day 30 at 696 hours (\pm 2 days) post-dose.

Measurements will be performed on the arm that is not connected to the ABPM system. Timepoints must not interfere with the ABPM measurements.

Pulse rate and respiration rate: Assessments will be performed as stated in the Table 16-1 at timepoints for blood pressure measurements. Pulse rate will be assessed in combination with both, supine and standing blood pressure measurements. Respiratory rate will be assessed at timepoints of supine blood pressure measurements.

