9.1.8 Procedures for Clinical Laboratory Samples

All samples will be collected in accordance with acceptable laboratory procedures. Laboratory samples (Table 9-1) will be taken as described in the Schedule of Events.

Table 9-1 Clinical Laboratory Assessments

Hematology	Serum Chemistry	Urinalysis
CBC with differential:	Hepatic function panel:	Routine urinalysis with
Hematocrit	Alanine aminotransferase	microscopic examination on
Hemoglobin	(ALT/SGPT)	positives(a):
mean corpuscular volume	alkaline phosphatase, serum	Color
(MCV)	aspartate aminotransferase	appearance,
mean corpuscular hemoglobin	(AST/SGOT)	specific gravity
(MCH)	bilirubin, direct	pН
mean corpuscular hemoglobin	bilirubin, total	protein
concentration (MCHC)	protein, total, serum	glucose
red cell distribution width	•	ketones
(RDW)	Renal function panel:	occult blood
percentage and absolute	Albumin, serum	leukocyte esterase
differential counts	BUN	nitrite
platelet count	BUN: creatinine ratio	bilirubin

red cell count (RBC) white blood cell count (WBC)	calcium, serum urobilinogen carbon dioxide, total chloride, serum creatinine, serum glucose, serum phosphorus, serum potassium, serum sodium, serum						
	Lipid panel: Cholesterol, total high-density lipoprotein (HDL) cholesterol low-density lipoprotein (LDL) cholesterol (calculated) triglycerides very low-density lipoprotein (VLDL) cholesterol (calculated)						
	Additional parameters: Amylase Lipase Calcitonin Lactic acid dehydrogenase (LDH) Gamma-Glutamyl Transferase Magnesium Uric Acid						

Diagnostic Screening

Serum/Plasma/Whole Blood	Urine	Breath
HBsAg	Drug Screen Profile	Alcohol breath test at
Anti-HCV	Amphetamines	timepoints stated in the SOE
HIV 1/2	Barbiturates	at the CRU
TSH(b)	Benzodiazepines	
PTT	cocaine (as benzoylecgonine)	
PT	methylenedioxymetamphetamines	
INR	opiates	
HbA1c	Oxycodon	
	phencyclidine (PCP)	
	propoxyphene (Darvon®)	
	tricyclic anti-depressants	
	Urine drug screen as stated in the	
	SOE via commercial kit at the	
	CRU.	
	Female Subjects Only	

Free fatty acid (FFA) C-reactive protein (CRP)

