16.0 APPENDIX

Table 16-1 Schedule of Events

ASSESSMENT	SCREEN		IN-HOUSE PERIOD								OUTPA VIS	F/U	
Visit/ Timepoint (Day)	- 28	-2	-1	1	2	3	4	5	6	7	10 (± 1)	17 (± 1)	30 (± 2)
IP Administration				X									
Informed consent	X												
Demography	X												
Medical history	X												
Sequestered in clinic/unit		X	X	X	X	X	X	X	X	X			
Physical examination (PE)	X												X
Abbreviated PE		X								X	X	X	
Hematology, serum chemistry, urinalysis	X		X	X		X				X		X	X
Amylase, Lipase	X		X		X	X	X	X	X		X	X	X
Calcitonin	X												X
Coagulation	X		X			X							
TSH	X												X
HbA1c	X												
Hep B, Hep C, HIV	X												
ADAbs, nAbs & anti-PEG			X									X	X
Pregnancy test (urine)		X									X	X	X
Pregancy test (serum)	X												
FSH if postmenopausal	X												
Urine drug screen & alcohol breath test	Х	X									X	X	X
Weight	X	X	X	X	X	X	X	X	X	X	X	X	X
Height, BMI	X												
Vital signs	X	X	X^1	X^1	X^1	X^1	X ¹	X ¹	X ¹	X ¹	X	X	X
Standardized meals		X	X	X	X	X	X	X	X	X			

ASSESSMENT	SCREEN	IN-HOUSE PERIOD									OUTPA VISI	F/U	
Visit/ Timepoint (Day)	- 28	-2	-1	1	2	3	4	5	6	7	10 (± 1)	17 (± 1)	30 (± 2)
IP Administration				X									
Record concomitant medications	X	X	X	X	X	X	X	X	X	X	X	X	X
Record AE'S	X	X	X	X	X	X	X	X	X	X	X	X	X
Injection site assessment				X^3	X	X	X	X	X	X			
12-lead ECG	X	$X^{2,7}$					$X^{2,7}$	X^7		X^7	X^7	X^7	X^7
Holter monitoring ⁴			X	X	X	X	X						
ABP monitoring ⁴		X	X	X	X	X	X						
PK assessment ⁵				X	X	X	X	X		X	X	X	X
Insulin, C- peptide, glucagon ⁶				X	X	X	X	X		X	X	X	X
GLP-1, GIP, amino acid panel ⁶				X	X	X	X	X		X	X	X	X
FPG	X		X ⁶	X^6	X ⁶	X^6	X^6	X^6	X^6	X^6	X^6	X^6	X ⁶
Lipid panel, incl. FFA	X			X ⁶		X ⁶				X ⁶		X^6	
Leptin ⁶				X		X				X		X	
CRP ⁶	C1.1 1		11.1	X		X		·	1	X	D 1	Х	1

 1 Measurements of blood pressure will be performed twice (morning and evening) on Day -1. On Day 1, measurements will be performed pre-dose and at 4, 8 and 12 hours post-dose, on Day 2 at 24 and 36 hours post-dose, on Day 3 at 48 hours, on Day 4 at 72 hours, on Day 5 at 96 hours, on Day 6 at 120 hours, on Day 7 at 144 hours post-dose with a sampling window of \pm 15 min for each timepoint.

Measurements of pulse rate and respiration rate will be performed at time points together with blood pressure measurements. Pulse rate will be assessed in combination with both, supine and standing blood pressure measurements. Respiration rate will be assessed at time points of supine blood pressure measurements.

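### Calcitonin and TSH are named in the primary laboratory endpoint, but after dosing they are sampled only on Day 30, so a change that resolves before then would be missed

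*Protocol*

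**What the plan says.** Section 5.1 makes laboratory abnormalities a primary safety endpoint and names five items: "Incidence of clinical laboratory abnormalities (including serum amylase, serum lipase, coagulation, thyroid stimulating hormone (TSH), serum calcitonin". The Study Summary and Table 12-1 repeat the list.

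Section 9.1.8 says that laboratory samples "will be taken as described in the Schedule of Events", which is Table 16-1. For the named items and routine chemistry, that table marks:

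| Row in Table 16-1 | Before dosing | After dosing |
|---|---|---|
| Amylase, lipase | Screening, Day -1 | Days 2 to 6, 10, 17, 30 |
| Coagulation | Screening, Day -1 | Day 3 |
| TSH | Screening | Day 30 |
| Calcitonin | Screening | Day 30 |
| Hematology, serum chemistry, urinalysis | Screening, Day -1 | Days 1, 3, 7, 17, 30 |

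The calcitonin row carries two marks and no others: "Calcitonin X X". Table 9-1, however, lists calcitonin among the serum chemistry parameters. It places TSH under diagnostic screening.

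On exposure, section 6.3 says that Cmax "is expected to be reached approximately 3 days after dosing". Section 4.3 gives half-lives of "42.7 to 85.6 hours in mice, 74.7 to 86.0 hours in rats, and 35.7 to 79.7 hours in dogs" and adds: "To date, no human studies have been conducted with HM15211". The last visit is "on Day 30 at 696 hours" (section 9.1.6), with a window of ±2 days. Section 4.5 allows an escalation decision once at least 6 subjects in a cohort, at least 4 of them on active drug, have completed Day 10.

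**The concern.** An incidence of abnormalities can count only what is sampled. For two of the five named items there is a single post-dose look, about four weeks after a single dose and long after the expected peak. Three things follow.

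- A change that comes and goes with exposure leaves no trace in the data.
- An abnormal Day 30 value has no earlier post-dose value beside it, so its onset cannot be dated and it cannot be set against concentration. The only pre-dose value is from Screening.
- The escalation review of a cohort can take place from Day 10 with no post-dose calcitonin or TSH result from that cohort. Section 6.4.1 has a stopping criterion based on similar clinically significant laboratory abnormalities in two or more subjects on HM15211. These two analytes cannot inform it before Day 28 at the earliest.

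A report of no calcitonin or TSH abnormalities would then describe the subjects after most of the exposure is expected to have passed. The statistical analysis plan cannot repair this, because the samples would not exist.

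**Working it through.** **Inputs.** Expected Tmax is about 72 h (section 6.3). Half-lives are 35.7 to 86.0 h in mice, rats and dogs (section 4.3). Day 30 is (30 − 1) × 24 = 696 h, which matches section 9.1.6; the window runs from 648 to 744 h. Day 7 is 144 h. The protocol states no residual-exposure figure, so there is none to reproduce.

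**Model.** One compartment with first-order absorption:

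C(t) ∝ exp(−ke·t) − exp(−ka·t), with ke = ln 2 / half-life.

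ka is solved so that Tmax = ln(ka/ke)/(ka − ke) = 72 h. The residual is C(t)/C(72).

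**Example at 86.0 h.** ke = 0.00806 and ka = 0.02202 per hour.

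- C(72) ∝ 0.5597 − 0.2049 = 0.3548
- C(144) ∝ 0.3133 − 0.0420 = 0.2713, and 0.2713/0.3548 = 76%
- C(696) ∝ 0.00366, and 0.00366/0.3548 = 1.03%

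**Results.**

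| Half-life (h) | Source | ke (per h) | ka (per h) | Residual at 144 h | Residual at 696 h |
|---|---|---|---|---|---|
| 35.7 | shortest animal value | 0.0194 | 0.0095 | 75% | 0.51% |
| 50 | inside the animal range | 0.0139 | 0.0139 | 74% | 0.17% |
| 86.0 | longest animal value | 0.0081 | 0.0220 | 76% | 1.03% |
| 120 | assumption | 0.0058 | 0.0274 | 80% | 3.4% |
| 168 | assumption | 0.0041 | 0.0330 | 84% | 8.7% |

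The residual is lowest in the middle of the animal range, where absorption and elimination rates are equal. Across the whole range it does not exceed about 1.0% at 696 h. With the visit window, the 86.0 h case gives 1.5% at 648 h and 0.7% at 744 h. More than 10% of Cmax would remain at 696 h only with a half-life above about 178 h, roughly twice the longest animal value.

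**Why not simple decay from the peak.** 624 h of pure decay is 624/35.7 = 17.5 or 624/86.0 = 7.3 half-lives, which would leave 0.0005% to 0.65%. That ignores drug still being absorbed after the peak. With a 35.7 h half-life and Tmax at 72 h, absorption must be slower than elimination (0.0095 against 0.0194 per hour), so the tail follows absorption. Simple decay therefore understates the residual at 696 h. It also gives 25% to 56% at 144 h, which is too low.

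**Age of the pre-dose value.** Screening may be 28 days before dosing, and Day 30 is 29 days after it: 28 + 29 = 57 days, or 59 at the end of the window.

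**Escalation timing.** Section 6.1 sets at least 10 days between the starts of consecutive dose levels. On that minimum, cohort 3 could start 20 days after cohort 1, before the earliest Day 28 sample of cohort 1.

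**The case against.** The strongest reply is that the document does not contradict itself. The endpoint is an incidence of abnormalities. It does not promise detection at Cmax or before escalation, and a pre-dose and an end-of-study value satisfy its wording. Section 4.3 reports no target organ in the 4-week toxicity studies, and the protocol gives no time course for either analyte. Screening limits bound both at entry, and pooled placebo subjects are followed on the same schedule. This stands as far as it goes: the point concerns a design choice, and whether a transient change after one dose is likely cannot be settled from the document. But the protocol itself named these two analytes in a primary endpoint and gave the other named items samples during exposure.

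Two provisions might seem to cover the gap. Table 9-1 lists calcitonin under serum chemistry, which is drawn on Days 1, 3, 7 and 17. However, section 9.1.8 defers timing to Table 16-1, where calcitonin has its own row. If the sponsor meant it to follow chemistry, that row needs correcting. Section 4.5 allows added sampling times if PK data suggest them, but commits to neither analyte.

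A reader might infer that the plan cannot show any effect on calcitonin or TSH, or that the laboratory endpoint as a whole fails. Neither follows. A change persisting to Day 30 would be seen, and the other named items are sampled during exposure.

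A reader might also infer that the drug is known to be gone by Day 30 in humans. The half-lives are animal values. Section 4.1 says that the Fc carrier "has an in vivo half-life of several weeks without effector functions", though that describes the carrier and not HM15211. If the human half-life proved much longer, more drug would remain on Day 30, but there would still be no sample before Day 28.

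The choice of baseline for analysis may properly sit in the statistical analysis plan. What the protocol fixes is that no pre-dose sample after Screening exists to choose.

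**Conclusion.** The point holds as a gap in sampling times for two of the five named items, and it is a cheap improvement. The schedule fact is exact and needs no model: there is no calcitonin or TSH value between dosing and the Day 30 (±2) visit.

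The size rests on three assumptions: animal half-lives carry over to humans, the peak falls at about 72 h, and a one-compartment curve is adequate. On these, about 0.5% of Cmax (shortest half-life) and 1.0% (longest) remain at 696 h, against about 75% and 76% at 144 h. With assumed human half-lives of 120 to 168 h, about 3.4% to 8.7% remains at 696 h. The direction is the same throughout: Day 7 sees substantial exposure and Day 30 sees little.

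The loss is limited to changes that resolve before Day 30, to the dating and exposure relation of an abnormal Day 30 value, and to escalation reviews held without these results.

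**What to change.** In Table 16-1, mark calcitonin and TSH on Day -1 and Day 7, using the chemistry draws already scheduled on those days, and keep Day 30. The Day -1 value provides a pre-dose reference closer to dosing than Screening. The Day 7 value gives one look during exposure, before the Day 10 visit; whether it is reported in time for the escalation review depends on laboratory turnaround, which the protocol does not state. Reconcile the calcitonin row of Table 16-1 with its listing under serum chemistry in Table 9-1, so that one schedule governs.

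The cost is 2 analytes × 2 days × about 40 subjects = about 160 assays, with no new visit or venepuncture. Some extra blood may be needed. Assay volumes are not stated, so this must be checked against the roughly 370 mL total in section 9.1.20. The rise to about 400 mL mentioned there is tied to unexpected sampling, an extended sampling period or retesting, and should not be taken as room for planned assays.
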